1. INTRODUCTION AND RATIONALE

1.1. Background

Migraine is a common and debilitating neurological disorder that affects approximately 15% of the adult population. It is characterized by moderate-to-severe episodic unilateral pulsating headaches that last for 4 to 72 hours. Typical characteristics of the headache are unilateral location, pulsating quality, moderate or severe headache pain intensity, aggravation by routine physical activity, and association with nausea and/or photophobia and phonophobia.¹

BHV-3000 (rimegepant) (PF-07899801) is a calcitonin gene-related peptide (CGRP) receptor antagonist in development for the acute treatment of migraine. The CGRP receptor is located within pain-signaling pathways, intracranial arteries and mast cells and its activation is thought to play a key role in migraine pathophysiology. For example, research and clinical studies have shown: serum levels of CGRP are elevated during migraine attacks, infusion of intravenous CGRP produces persistent pain in migraine sufferers and non-migraine sufferers, and treatment with anti-migraine drugs normalize CGRP levels. Additionally, multiple clinical studies show that small molecule CGRP receptor antagonists, which inhibit the binding of endogenous CGRP to CGRP receptors, are effective in aborting migraine attacks. Treatment with a CGRP receptor antagonist is believed to relieve migraine through the possible mechanisms of 1) blocking neurogenic inflammation, 2) decreasing artery dilation, and 3) inhibiting pain transmission. There is widespread agreement that this new approach avoids the cardiovascular effects produced by active vasoconstriction associated with the current standard triptan therapy (non-selective 5-HT_{1B/1D} agonists (e.g., sumatriptan [ImitrexTM])).

1.1.1. Clinical Experience

Rimegepant (Nurtec[®] ODT, Vydura, BHVS-3000 [PF-07899801]) is an oral, small molecule, calcitonin gene-related peptide (CGRP) receptor antagonist approved in the United States (US) and the European Union (EU) for the acute treatment of migraine and the preventive treatment of episodic migraine in adults.^{2,3} Rimegepant is currently in development for the acute and preventive treatment of migraine in pediatric subjects, as well as for the treatment of refractory trigeminal neuralgia, the acute treatment of chronic rhinosinusitis (CRS), and temporomandibular disorders (TMD)

Please refer to the most up to date Investigator's Brochure for additional safety information.

1.1.2. Product Development Background

Details of the clinical and preclinical studies are provided in the current Investigator Brochure. A summary of the relevant data to the study are presented below.⁴

Rimegepant is approved for the acute treatment and prevention of episodic migraine in the United States (US), United Kingdom (UK), and European Union (EU) and is well tolerated when given as a single oral dose of 75 mg for the acute treatment of migraine and at a dose of 75 mg every other day (EOD) for the prevention of episodic migraine. The efficacy and tolerability of rimegepant for the acute and preventive treatment of migraine in the pediatric

population is currently being evaluated. In this study, rimegepant is used in adults at the dose (75 mg) and in the indication (acute treatment of migraine) which are covered by the Marketing Authorization.

As of 26 February 2024, it is estimated that 12,135 participants have been involved in rimegepant clinical development studies and approximately 6630 participants have received rimegepant at any dose. Collectively, the current data demonstrates a favorable benefit-risk profile for rimegepant in the acute and preventive treatment of migraine. More detailed information about the known and expected benefits and risks and reasonably expected AEs of rimegepant may be found in the Investigator's Brochure, which is the SRSD for this study.

1.2. Benefit/Risk Assessment

Rimegepant represents an advancement in migraine therapeutics, providing the first CGRP antagonist to demonstrate benefit for both the acute treatment and prophylaxis of migraine.

Rimegepant appears to be generally safe and well tolerated when given as single oral doses from 75 mg up to the maximum dose of 1500 mg and multiple oral doses up to the maximum daily dose of 600 mg for 14 days.

Broad and sustained efficacy of rimegepant 75 mg was demonstrated in 3 previously completed Phase 3 studies (BHVS3000-301, BHVS3000-302 and BHVS3000-303). Statistically significant efficacy was demonstrated on the co-primary endpoints of freedom from pain, and freedom from most bothersome symptom at 2 hours post-dose. Also, in all 3 studies, significant results were achieved on photophobia freedom, phonophobia freedom, and pain relief at 2 hours post-dose. Similar results were demonstrated in the BHVS3000-310 study recently completed in China and Korea. In the Phase 2/3 placebo-controlled study (BHVS3000-305) for the preventive treatment of migraine, rimegepant at a dose of 75 mg every other day (EOD) demonstrated statistically significant superiority to placebo on the primary endpoint of change from the observation period in the mean number of migraine days per month on treatment in the last month of the double-blind treatment phase.

A multicenter open-label, long-term study (BHVS3000-201) was conducted to evaluate the safety and tolerability of rimegepant 75 mg tablet taken as needed (up to one tablet per day upon onset of a migraine of mild, moderate, or severe intensity) for the acute treatment of migraine for up to 52 weeks. This multiple-dose, long-term study of rimegepant 75 mg administered for up to 52 weeks confirmed the favorable safety profile across a variety of safety endpoints, including AE assessments, clinical laboratory testing including LFTs, vital signs, and ECGs. Safety data from the double-blind treatment and the open-label extension phases of the pivotal Phase 2/3, randomized, double-blind, placebo-controlled preventive treatment of migraine study (BHVS3000-305) support a favorable safety profile of rimegepant 75 mg administered EOD for the preventive treatment of migraine. Rimegepant 75 mg administered EOD + PRN for up to 52 weeks in the open-label phase was well tolerated, with no new safety signals observed in the open-label-extension phase.

Across the rimegepant clinical development program, low frequency of events of hypersensitivity (including urticaria, angioedema, anaphylactic reaction, and rash) were

observed. No AEs representing serious cutaneous manifestation of hypersensitivity (e.g, Stevens-Johnson syndrome) were observed.

Across the rimegepant clinical development program, no cases of Hy's Law were identified, and there was no signal of DILI due to rimegepant when administered up to once daily PRN for up to 52 weeks of treatment.

There are no adequate data on the developmental risk associated with the use of rimegepant in pregnant women. Both women of childbearing potential, as well as those who are of non childbearing potential, may be enrolled given the availability of embryo-fetal development (EFD) nonclinical toxicity studies with rimegepant. Contraception method is required, and measures will be taken to limit the risk of pregnancy in the female population of childbearing potential enrolled (See [Appendix 5](#)). The potential risk of exposure to rimegepant in a sexual partner of a male subject in this study via ejaculate is low, and therefore no contraception (condom) use in male subjects is warranted. The calculated safety margin is ≥ 100 -fold between the estimated partner exposure due to seminal transfer and the NOAEL for serious manifestations of developmental toxicity in nonclinical studies. The safety margin of 100-fold is based on applying a 10-fold safety factor for interspecies extrapolation and a 10-fold safety factor for susceptible populations.⁵

Subjects undergo regular pregnancy testing throughout the duration of the study. Although no safety issues in clinical trials of rimegepant were observed, cardiovascular events, cerebrovascular events, hypertensive events, and serious gastrointestinal events associated with constipation are reviewed in each aggregate report per FDA request. None of these reviews have detected any safety signal associated with these events. Subjects are excluded if there is uncontrolled, unstable, or recently diagnosed cardiovascular disease or hypertension. Subjects are monitored through multiple safety endpoints, including AE assessments, clinical laboratory testing, vital signs and ECGs.

Review of all data available, including post-marketing information, nonclinical, clinical, and scientific literature data, demonstrates a favorable benefit-risk profile for the use of rimegepant in this study. More detailed information about the known and expected benefits and risks and reasonably expected AEs of rimegepant may be found in the Investigator Brochure, which is the SRSD for this study.

1.3. Study Rationale

Rimegepant is approved medication for the acute treatment of migraine attacks and preventive treatment of episodic migraine. Effectiveness for the acute treatment of migraine was initially demonstrated in a Phase 2b double-blind, randomized, placebo-controlled, dose-ranging study where rimegepant at 75 mg showed efficacy on all four traditional endpoints: pain, nausea, photophobia, and phonophobia.¹

Efficacy was confirmed for the acute treatment of migraine in three pivotal single-attack Phase 3 trials using the current registrational co-primary endpoints of migraine headache pain freedom and freedom from most bothersome symptom at 2 hours postdose. Rimegepant

effectiveness for the preventive treatment of episodic migraine was demonstrated in a Phase 2/3 double-blind, randomized, placebo-controlled study of rimegepant 75 mg dosed every other day (EOD).⁶ EOD dosing was also well tolerated with no signals of medication-overuse headache, abuse potential, cardiovascular events, or hepatotoxicity.

Rimegepant represents an alternative treatment option for migraine sufferers who are not well served by existing standard of care (e.g., triptans), due to either a poor or inconsistent therapeutic response, prior intolerance, or due to the presence of contraindications. Subgroup analysis of subjects enrolled in Phase 3 pivotal trials who were identified having discontinued one or more triptans indicated that rimegepant demonstrated a similar degree of efficacy as for the general study population. Therefore, the primary aim of this study is to confirm the efficacy of rimegepant in a population deemed unsuitable for triptan use and in whom an alternative treatment option would be most advantageous.

1.3.1. Study Design Rationale

This study is being conducted to evaluate the efficacy and tolerability of rimegepant for the acute treatment of migraine among adults considered unsuitable for triptan use because of prior intolerance, lack of efficacy or contraindication (including a history of clinically relevant cardiovascular disease). The double-blind, placebo-controlled, parallel group design to assess the efficacy and tolerability of rimegepant in this population in a primary migraine attack is in accordance with international guidelines for such an evaluation.⁷ Additional information on the effectiveness and safety of rimegepant will also be obtained across additional attacks when used as needed in the 12-week open-label extension. The inclusion of the 12-week OLE Phase allows for the evaluation of safety and tolerability of rimegepant across multiple migraine attacks in a population of triptan-unsuitable adults. In addition, the OLE Phase allows for the potential to evaluate consistency of effect (as measured by improvement in quality of life [MQoL Question 16]), at the population level, among adults in need of effective alternative treatments for the management of acute migraine.

1.3.2. Dose Selection Rationale

The Phase 2b dose-ranging study CN170003 established that rimegepant 75 mg is the minimum effective dose for the acute treatment of migraine. The three Phase 3 studies BHVS000-301, BHVS000-302, and BHVS000-303 confirmed this efficacy using the current registrational endpoints for acute treatment of migraine. The current study will evaluate the efficacy and tolerability of the acute treatment of multiple migraine attacks in adults unsuitable for triptan use.

1.3.3. Research Hypothesis

Rimegepant is a safe and effective treatment for acute treatment of migraine in adults who are unsuitable for triptan use because of prior intolerance, lack of efficacy, or contraindication (including a history of clinically relevant cardiovascular disease).

2. STUDY OBJECTIVES

2.1. Primary Objectives

To compare the efficacy of rimegepant with placebo in the acute treatment of migraine, as measured by migraine headache pain relief at 2 hours postdose during the DBT Phase.

2.2. Secondary Objectives

2.2.1. Key Secondary Objectives

1. To compare rimegepant with placebo for migraine headache pain freedom at 2 hours postdose during the DBT Phase.
2. To compare rimegepant with placebo for rescue medication use within 24 hours postdose during the DBT Phase.
3. To compare rimegepant with placebo for return to normal function, as measured by the functional disability scale, at 2 hours postdose during the DBT Phase.
4. To compare rimegepant with placebo for sustained return to normal function, as measured by the functional disability scale, from 2 to 24 hours postdose during the DBT Phase.
5. To compare rimegepant with placebo for sustained return to normal function, as measured by the functional disability scale, from 2 to 48 hours postdose during the DBT Phase.
6. To compare rimegepant with placebo for sustained migraine headache pain relief from 2 to 24 hours postdose during the DBT Phase.
7. To compare rimegepant with placebo on sustained migraine headache pain relief from 2 to 48 hours postdose during the DBT Phase.
8. To compare rimegepant with placebo for sustained migraine headache pain freedom from 2 to 24 hours postdose during the DBT Phase.
9. To compare rimegepant with placebo for sustained migraine headache pain freedom from 2 to 48 hours postdose during the DBT Phase.
10. To compare rimegepant with placebo for freedom from the most bothersome symptom (MBS) associated with migraine at 2 hours postdose during the DBT Phase.

2.2.2. Other Secondary Objectives

1. To evaluate reliability of rimegepant effect in the OLE Phase, as measured by Migraine Quality of Life Questionnaire (MQoL) Question 16 (overall change in migraine symptoms since taking study medication) at 24 hours postdose in the DBT Phase and after each of the first 5 qualifying migraine attacks in the OLE Phase.

2. To evaluate the mean change from historical baseline in the number of migraine days per month by headache pain intensity (total; moderate or severe) in each month and over the entire OLE Phase.
3. To evaluate the proportions of subjects with $\geq 50\%$ reduction from historical baseline in the number of migraine days per month by headache pain intensity (total; moderate or severe) in each month and over the entire OLE Phase.
4. To evaluate the frequencies of adverse events by intensity, serious adverse events, adverse events leading to study drug discontinuation, and grade 3 to 4 laboratory test abnormalities during the DBT and OLE Phases.
5. To evaluate the mean change from baseline in the Migraine Interictal Burden Scale (MIBS) score over time during the OLE Phase.

2.3. Exploratory Objectives

1. To evaluate the Migraine Quality of Life Questionnaire (MQoL) at 24 hours postdose during the DBT Phase
2. To evaluate the Migraine Quality of Life Questionnaire (MQoL) at 24 hours postdose after each of the first 5 qualifying migraine attacks during the OLE Phase.
3. To evaluate migraine headache pain relief at all scheduled time points postdose during the DBT Phase.
4. To evaluate migraine headache pain freedom at all scheduled time points postdose during the DBT Phase.
5. To evaluate MBS freedom at all scheduled time points postdose during the DBT Phase.
6. To evaluate return to normal function, as measured by the functional disability scale, at all scheduled time points postdose during the DBT Phase.
7. To evaluate photophobia freedom at all scheduled time points postdose during the DBT Phase.
8. To evaluate phonophobia freedom at all scheduled time points postdose during the DBT Phase.
9. To evaluate nausea freedom at all scheduled time points postdose during the DBT Phase.
10. To evaluate pain relapse from 2 to 48 hours postdose during the DBT Phase.
11. To evaluate time to migraine headache pain relief through 48 hours postdose during the DBT Phase.

12. To evaluate the mean number of acute migraine medication (rescue or non-rescue) days per month in each month and over the entire OLE Phase.
13. To evaluate the proportion of subjects who use rescue medication after each of the first 5 qualifying migraine attacks during the OLE Phase.
14. To evaluate the frequencies of hepatic-related adverse events and hepatic-related adverse events leading to study drug discontinuation in subjects treated with rimegepant during the DBT and OLE Phases.
15. To evaluate the mean changes from baseline in the Migraine-Specific Quality-of-Life Questionnaire v2.1 (MSQ) domain scores at Week 12 of the OLE Phase.
16. To evaluate the frequency of liver function test (LFT) elevations (AST, ALT, or total bilirubin) based on fold changes above ULN in subjects treated with rimegepant during the DBT and OLE Phases.
17. To evaluate primary and key secondary efficacy endpoints during the DBT Phase and high-level safety endpoints during the DBT and OLE Phases by history of clinically relevant CV disease (yes, no).
18. To evaluate primary and key secondary efficacy endpoints during the DBT Phase by history of documented failure to ≥ 2 triptan medications with ≥ 1 failure due to lack of efficacy (yes, no).

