- In the OLE Phase, lasting up to 12 weeks, subjects will be able to take up to 1 tablet of open-label study drug (75 mg ODT rimegepant) per calendar day as needed for acute treatment of migraine for a maximum of 18 doses per month (month is 28 days).
 - ***During the OLE Phase***
 - Subjects are to use open-label study drug as the first treatment of migraine attacks of moderate or severe headache pain intensity, and should not take acute migraine medication before taking open-label study drug
 - In association with each of the ***First 5 Qualifying Migraine Attacks***, subjects are required to complete the MQoL Questionnaire within the eDiary at 24 hours after dosing with open-label study drug
 - If migraine-associated symptoms persist beyond 2 hours after dosing with open-label study drug, subjects may use permitted acute migraine medication for the purposes of rescue, as needed and in accordance with the standard of care. *All dosing of rescue medication (permitted or exclusionary), is to be recorded on the Rescue Medication paper diary.*

Number of Subjects:

Approximately 600 subjects will be randomized in a 1:1 ratio to blinded rimegepant or matching placebo in the DBT Phase. Randomization will be stratified by history of clinically relevant cardiovascular (CV) disease (yes, no). In addition, randomization of subjects in the

CV subgroup (“yes” category) will be capped at 15%. In the OLE Phase, the study drug will be 75 mg ODT of open label rimegepant as needed, up to once per calendar day.

Study Population:

The study will recruit subjects ≥ 18 years of age with a minimum 1 year documented history of migraine attacks (with or without aura) consistent with a diagnosis according to the International Classification of Headache Disorders, 3rd Edition.

Per self-report, with confirmation from Investigator/ supporting medical record, subjects must have:

1. Migraine attacks present for more than 1 year with the age of onset prior to 50 years of age.
2. Migraine attacks, on average, lasting about 4 - 72 hours if untreated.
3. 4 to 14 migraine days per month on average across the 3 months prior to the Screening Visit (month is defined as 28 days for the purpose of this protocol).
4. Less than 15 headache days (migraine or non-migraine) per month in each of the 3 months prior to the Screening Visit and throughout the Screening Phase
5. Less than 7 non-migraine headache days per month, on-average, across the 3-months prior to the Screening Visit

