9.1. Sample Size

It is anticipated that about 90% of the 300 subjects randomized to each treatment group will have a migraine in the allotted time period of the DBT Phase, resulting in approximately 270 subjects evaluable for efficacy in each treatment group. The sample size calculation is based on pooled results from Phase 3 single-dose migraine studies BHV3000-301, BHV3000-302, and BHV3000-303. Pooled response rates for migraine headache pain relief at 2 hours postdose were 57.9% for rimegepant 75 mg and 43.9% for placebo in these studies.

A total sample size of 540 evaluable subjects (270 per treatment group) will provide approximately 90% power for the primary endpoint of migraine headache pain relief at 2 hours postdose in the DBT Phase. This is based on a chi-square test with a 2-sided alpha level of 0.05 and assumes that the true response rates in the subjects unsuitable for triptan use will be equivalent to the overall pooled response rates above.

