4.3 Subgroups

Subgroup tables present results by subgroup level and overall for subjects with nonmissing subgroup level data.

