The overall summary table of treatment comparisons of all primary and key secondary efficacy endpoints during the DBT Phase is also produced by subgroup level for all efficacy subgroups of interest described in Section 4.3.1. Separate tables are provided for each subgroup. Analyses are performed unstratified, and p-values are presented only for descriptive purposes. Results support exploratory objectives #17 and #18.

Forest Plot of Primary and Key Secondary Efficacy Endpoints During the DBT Phase

The forest plot of treatment comparisons of all primary and key secondary efficacy endpoints during the DBT Phase is provided for the DBT efficacy analysis set, and is based on the overall summary. The plot displays the following statistics:

- Response rate (i.e., “n/N” and percentage) by treatment group
- Stratified percentage difference between treatment groups (rimegepant – placebo) and 95%CI.

Percentage differences with p-values that are determined to be significant based on the testing hierarchy are identified. Note that the plot displays results for no rescue medication use within 24 hours postdose so that positive percentage differences favor rimegepant for these key secondary endpoints.

By-Subject Listing of Primary and Key Secondary Efficacy Endpoints During the DBT Phase

The by-subject listing of primary and key secondary efficacy endpoints during the DBT Phase is provided for the full analysis set that includes first DBT rescue medication date/time (see Section 7.1), time to first DBT rescue medication use in hours (see Section 6.3.3.2), migraine headache pain intensity at the time of DB study drug dosing, MBS before DB study drug dosing, and reason(s) for exclusion from the DBT efficacy analysis set (randomized more than once; not treated with DB study drug; treated with DB study drug but no qualifying migraine attack at the time of DB study drug dosing; qualifying migraine attack at the time of DB study drug dosing but no postdose efficacy data in the DBT Phase); note that the last 3 reasons are mutually exclusive.

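### SAP 6.3.1.1 reports the efficacy subgroups as p-values within each level and plans no estimate of the difference between levels; at the 15% cap on CV history, an identical effect on the primary endpoint would give CV-no significant and CV-yes not significant in about 65% of trials

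*Protocol*

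**What the plan says.** Protocol 2.3 lists two exploratory subgroup objectives. Objective 17 is "To evaluate primary and key secondary efficacy endpoints during the DBT Phase and high-level safety endpoints during the DBT and OLE Phases", by CV history. Objective 18 covers the primary and key secondary efficacy endpoints by history of failure on two or more triptans with at least one failure for lack of efficacy. SAP 4.3.1 names the same two efficacy subgroups.

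SAP 4.3 sets the general layout: "Subgroup tables present results by subgroup level and overall for subjects with nonmissing subgroup level data". SAP 6.1.1.1 has the efficacy subgroup tables follow the main efficacy tables, with a row and a page break for each level. SAP 6.3.1.1 repeats the overall summary table (response rate with CI per arm, difference, 95% CI and p-value) for each level, and adds: "Analyses are performed unstratified, and p-values are presented only for descriptive purposes".

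Neither document specifies a between-level contrast, an interaction term or a homogeneity test for these subgroups. The forest plot in SAP 6.3.1.1 covers endpoints in the whole DBT efficacy set, not subgroup levels.

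Protocol 4.1 and 7.1.6 cap CV-yes subjects at 15% of randomization. Neither document gives an expected split for triptan failure.

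**The concern.** When two levels differ greatly in size, their separate p-values say more about the sizes than about whether the drug works differently. The cap makes that imbalance known in advance for CV history. A table with a small p-value in CV-no and a large one in CV-yes invites a comparison that those p-values cannot support, and the quantity that would support it is not in the planned output.

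CV history is the only stratification factor, and Protocol Appendix 4 defines the CV subgroup partly for subgroup analysis, so these tables are likely to be read. With 11 primary and key secondary endpoints, two subgroups and two levels each, 11 × 2 × 2 = 44 within-level p-values would be printed. None of them addresses a difference between levels.

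**Working it through.** **Inputs.** Protocol 9.1 gives the rates: "Pooled response rates for migraine headache pain relief at 2 hours postdose were 57.9% for rimegepant 75 mg and 43.9% for placebo". It gives the size and power: "A total sample size of 540 evaluable subjects (270 per treatment group) will provide approximately 90% power for the primary endpoint". The test is stated as follows: "This is based on a chi-square test with a 2-sided alpha level of 0.05". The 15% cap and 1:1 allocation are in Protocol 7.1.6. Assumptions made here: the same true rates in both levels, and an evaluable share equal to the randomized share.

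**Formula.** With n per arm, d = 0.579 − 0.439 = 0.140 and mean rate 0.509:

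power = Φ{[d√n − 1.96·√(2 × 0.509 × 0.491)] / √(0.579 × 0.421 + 0.439 × 0.561)} = Φ{[0.140√n − 1.386] / 0.700}

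**Reproducing the plan's figure.** At n = 270: (2.300 − 1.386)/0.700 = 1.31, giving 90.4%. This agrees with the stated figure of approximately 90%.

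**CV history at the cap.**

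- CV-yes: n = 0.15 × 270 = 40.5 per arm; (0.891 − 1.386)/0.700 = −0.71; power 24.0%.
- CV-no: n = 0.85 × 270 = 229.5 per arm; (2.121 − 1.386)/0.700 = 1.05; power 85.3%.
- The levels are independent, so P(CV-no significant, CV-yes not) = 0.853 × (1 − 0.240) = 64.9%.
- P(both significant) = 0.853 × 0.240 = 20.5%.

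A simulation of 400,000 trials with the unpooled Wald test, at 40 and 230 per arm, gave 64.2% for the split pattern.

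**If CV-yes falls short of the cap.**

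| CV-yes share | Power, CV-yes | Power, CV-no | CV-no significant, CV-yes not |
|---|---|---|---|
| 15% | 24.0% | 85.3% | 65% |
| 10% | 17.4% | 87.2% | 72% |
| 5% | 10.7% | 88.9% | 79% |

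The last two rows use the normal approximation at very small n and are rough. At a 10% share (27 and 243 per arm) the Wald simulation gave 67%.

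**Precision of the levels and of the contrast at the cap.** The per-subject variance sum is 0.490.

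- SE in CV-yes = √(0.490/40.5) = 0.110; 95% half-width 21.6 points.
- SE in CV-no = √(0.490/229.5) = 0.046; 95% half-width 9.1 points.
- SE of the contrast = √(0.110² + 0.046²) = 0.119; 95% half-width 1.96 × 0.119 = 23.4 points.
- Gap detectable with 80% power = (1.96 + 0.84) × 0.119 = about 33 points.

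In the same simulation, with identical effects, the 95% CI of the contrast excluded zero in about 5.6% of trials.

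**The case against.** The case for leaving the plan alone has real weight. Objectives 17 and 18 ask to evaluate endpoints by level, whereas the protocol writes of comparing when it wants a comparison. SAP Table 4 defines the matching summary as the percentages and treatment difference, and SAP 6.3.1.1 delivers these with CIs. A reader might infer that the plan fails its own objective; it does not. The p-values are labelled descriptive and lie outside the testing hierarchy, so type I error is unaffected. The CV-yes CI, about ±22 points, already shows how little that level can say, and a careful reader could derive the contrast from the table.

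Three further limits stand. The 65% is the probability of a pattern of p-values, not of someone misreading it. It applies to the primary endpoint by CV history at the cap. The ten key secondary endpoints have no assumed rates, and some use a smaller set of subjects. The cap also acts at randomization, while SAP 6.2.5.1 forms the subgroup mainly from CRF data, so the analysed share may differ.

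The objection does not explain what the within-level p-values add. The difference and CI already describe each level, and the p-value contributes only a significance cut whose outcome depends on level size. Nor should readers have to construct the contrast themselves.

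**Conclusion.** The point holds as a cheap improvement to an exploratory analysis. SAP 6.3.1.1 prints within-level p-values and no between-level estimate. At the 15% cap, with 540 evaluable subjects and the plan's rates in both levels, an identical effect gives the split pattern on the primary endpoint in about 65% of trials, and more often if CV-yes is smaller.

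Two stronger readings are not supported. One is that the same figure applies to every subgroup table: the triptan-failure split is not stated, so only the missing contrast is established there. The other is that the trial leaves its research hypothesis untested in CV patients: that hypothesis concerns the whole triptan-unsuitable population and is tested in the full DBT efficacy set, stratified by CV history, with no confirmatory subgroup claim planned.

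The Core SAP and the mock table document were not available. The study SAP does not refer to the Core SAP for the efficacy subgroup comparison.

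**What to change.** In SAP 6.3.1.1, for the efficacy subgroup tables:

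- Remove the within-level p-values. Keep n/N, percentages, treatment difference and 95% CI for each level.
- Add the between-level contrast, at least for the primary endpoint: the difference in the yes level minus the difference in the no level, with 95% CI and SE = √(SE_yes² + SE_no²).
- Do not add an interaction p-value. Across 11 endpoints and two subgroups there would be 22 of them. At the cap the primary-endpoint test has 80% power only for a gap of about 33 points, and a non-significant result could be misread as proof of equal effect.
- State that neither effect, nor lack of effect, nor equality of effect is to be concluded from a single level or from a wide contrast CI.

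The cost is SAP wording and one row per endpoint covered, built from standard errors already computed. Design, data collection and alpha do not change. The downside is an imprecise contrast, with a half-width of about 23 points for the primary endpoint at the cap.
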